6.1.1. Part A Efficacy Analyses Considerations

Continuous endpoint

All Part A continuous efficacy endpoints will be analyzed using the following described method, unless otherwise specified.

A Mixed Effect Model Repeat Measurement (MMRM) model will be used as the primary method to analyze endpoint of interest using treatment group (BIIB059 450 mg vs. placebo), study visit (week 2, 4, 8, 12, 16, 20, 24), baseline corticosteroid usage level (≤ 10 mg, >10 mg), region (USA, Asia, Latin America & Europe), study visit-by-treatment interaction, baseline value of the endpoint, and baseline-by-visit interaction as fixed effect covariates. An unstructured covariance matrix will be used to model the within-patient variance-covariance errors. If the unstructured covariance structure matrix results in a lack of convergence, the heterogeneous Toeplitz covariance structure followed by the heterogeneous first-order autoregressive covariance structure will be used. The Kenward-Roger approximation will be used to estimate the denominator degrees of freedom. The primary treatment comparison will be the difference between the BIIB059 450 mg dose and placebo at the end of the Week 24

CONFIDENTIAL

The information contained herein may not be used, disclosed, or published without the written consent of Biogen MA Inc.

 Biogen	Statistical Analysis Plan 230LE201	<V 2.0>
--	---	----------------------

visit. Handling of missing data and data from treatment failures subjects is provided in [Section 6.6](#).

Binary endpoint

The binary endpoints will be analyzed using logistic regression with covariates of treatment (BIIB059 450 mg vs. placebo), baseline corticosteroid usage level (≤ 10 mg, >10 mg) and region (USA, Asia, Latin America & Europe). For binary endpoints related to CLASI-A score, CLASI-A score (≤ 10 vs. >10) will be added to the above covariates list. For endpoints dichotomized from a continuous endpoint (such as PGA VAS < 1 point increase) the baseline of the continuous endpoint will be added to the above covariates list. The odds ratio, its 95% CI and the p-value for BIIB059 450 mg dose compared to placebo will be presented. Early discontinuation(s) and/or treatment failures will be handled using non-responder imputation approach as discussed in [Section 6.6](#).

[REDACTED]

[REDACTED]

[REDACTED]

[REDACTED]

[REDACTED]

[REDACTED]

[REDACTED]

[REDACTED]

6.1.2. Part B Efficacy Analyses Considerations

Continuous endpoint

All Part B continuous efficacy endpoints will be analyzed using the following described method, unless otherwise specified.

A Mixed Effect Model Repeat Measurement (MMRM) model will be used as the primary method to analyze endpoint of interest using treatment group, study visit (week 2, 4, 8, 12, 16),

CONFIDENTIAL

The information contained herein may not be used, disclosed, or published without the written consent of Biogen MA Inc.

 Biogen	Statistical Analysis Plan 230LE201	<V 2.0>
--	---	----------------------

study visit-by-treatment interaction, DLE (Yes/No), CLASI-A score (≤ 10 vs. > 10), baseline value of the endpoint and baseline-by-visit interaction as fixed effect covariates. An unstructured covariance matrix will be used to model the within-patient variance-covariance errors. If the unstructured covariance structure matrix results in a lack of convergence, the heterogeneous Toeplitz covariance structure followed by the heterogeneous first-order autoregressive covariance structure will be used. The Kenward-Roger approximation will be used to estimate the denominator degrees of freedom. The primary treatment comparison between each BIIB059 treated group and placebo will be at the end of the Week 16. Handling of missing data and data from treatment failures subjects is provided in [Section 6.6](#).

Binary endpoint

The binary endpoints will be analyzed using logistic regression with covariates of treatment and DLE (Yes/No) and CLASI-A score (≤ 10 vs. > 10). For binary endpoints dichotomized from a continuous endpoint (such as PGA VAS < 1 point increase, the baseline of the continuous endpoint will be added to the above covariates list. The odds ratio, its 95% CI and the p-value for each BIIB059 dose compared to placebo will be presented. Early discontinuation(s) and/or treatment failures will be handled using non-responder imputation approach as discussed in [Section 6.6](#).

[REDACTED]

[REDACTED]

[REDACTED]

[REDACTED]

[REDACTED]

[REDACTED]

Censoring rules: Subjects who do not experience an event by Week 16 or early termination will be censored at the date of last assessment during the treatment period. The start date for calculation of day to censor or event will be the date of first dose.

CONFIDENTIAL

The information contained herein may not be used, disclosed, or published without the written consent of Biogen MA Inc.

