¹⁶ Pharmacokinetic evaluations will be conducted as follows: Study Day 1 (predose -1 h and post-dose 4 h ± 1 h), Day 8 (any time during visit), Day 29 (predose -1 h and postdose 4 h ± 1 h), Day 85 (predose -1 h and postdose 4 h ± 1 h), Day 113 (predose -1 h), and Day 169 (any time during visit). During the Follow-up Period, 1 sample will be collected on Days 197 and 253 (any time during the visit) [Table 3]. The time and date of PK sample collection and BIIB059 dose should be recorded in the eCRF.

²¹ Vaccine-related immunoglobulin titers for tetanus, diphtheria, and *Pneumococcus* will be collected.

CONFIDENTIAL

The information contained herein may not be used, disclosed, or published without the written consent of Biogen MA Inc.

Table 2: Schedule of Activities Part B

	Screening Period	Treatment Period							Follow-up Period ¹		
		0	1	2	4	8	12	16/ ET	FU4	FU8	FU12
Study Week	Within 4 Weeks Prior to Randomization	1 ³ (±2D)	8 (±2D)	15 ³ (±2D)	29 ³ (±3D)	57 ³ (±3D)	85 ³ (±3D)	113 (±3D)	141 (±5D)	169 (±5D)	197 (±5D)
Tests and Assessments ^{2,3}											
Informed Consent Form(s)	X										
Inclusion/Exclusion Criteria	X	X									
Randomization		X									
Demographic Data	X										
CLE, SLE and Other Medical History	X										
Documentation of SLE by ACR Criteria	X										
12-lead ECG ⁴	X							X			
Chest x-ray ⁵ (if required by local regulation)	X										
Tuberculosis Test ⁶	X										
Serum Virology (HIV, Hepatitis B and C) RNA	X										
Urine Drug Screen	X										
Serum Pregnancy Test	X										
Urine Pregnancy Test ⁷		X		X	X	X	X	X	X	X	X
Physical Examination, Weight, Height ⁸	X	X	X	X	X	X	X	X	X		X
Vital Signs ⁹	X	X	X	X	X	X	X	X	X	X	X
CLASI ¹⁰		X	X		X	X	X	X			X

CONFIDENTIAL

The information contained herein may not be used, disclosed, or published without the written consent of Biogen MA Inc.

	Screening Period	Treatment Period							Follow-up Period ¹		
		0	1	2	4	8	12	16/ ET	FU4	FU8	FU12
Study Week	Within 4 Weeks Prior to Randomization	1 ³	8 (±2D)	15 ³ (±2D)	29 ³ (±3D)	57 ³ (±3D)	85 ³ (±3D)	113 (±3D)	141 (±5D)	169 (±5D)	197 (±5D)
Tests and Assessments ^{2,3}											
Physicians Global Assessment of SLE (VAS) ^{11,12}	X	X		X	X	X	X	X			
Skin photography of target lesion ¹³	X	X			X			X			
Study treatment administration ¹⁴		X		X	X	X	X				
Corticosteroid Diary ¹⁵		X	X	X	X	X	X	X	X	X	X
Laboratory Assessment											
Hematology	X	X		X	X	X	X	X	X		X
Blood Chemistry	X	X		X	X	X	X	X	X		X

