⁶ Testing to be performed locally. Indeterminate Quantiferon or T-SPOT tests may be repeated once, and will be considered positive if retest results are positive or indeterminate. Subjects with documented BCG vaccination must perform a tuberculosis test at Screening and will be excluded if they exhibit skin induration ≥5 mm or a positive Quantiferon or positive or borderline T-SPOT (Elispot) test.

⁷ To be performed locally.

⁸ Height should be measured only once; i.e., at the Day 1/baseline Visit.

⁹ Vital signs include seated arterial blood pressure, heart rate, and oral body temperature.

¹⁰ CLASI will be assessed by the Investigator or a trained designee at all assessments (Section 19.2.2). CLASI scores at Screening will be verified by an Independent CLASI Adjudicator to confirm eligibility.

[REDACTED]

[REDACTED]

[REDACTED]

¹⁴ Following administration of study treatment, subjects should remain at the study center for 1 hour to be observed for the development of potential allergic or anaphylactic reactions.

CONFIDENTIAL

The information contained herein may not be used, disclosed, or published without the written consent of Biogen MA Inc.

¹⁵ Subject paper diaries for recording corticosteroid use will be distributed on Day 1, reviewed with site staff at each study visit, and collected by the study site at the final study visit.

¹⁶ Only for subjects with prior B cell directed therapies within 52 weeks of Screening; this test should be performed at a central laboratory.

¹⁷ Pharmacokinetic evaluations will be conducted as follows: Day 1 (pre-dose -1 h and post-dose 4 h \pm 1 h), Day 8 (any time during the visit), Day 29 (predose -1 h and postdose 4 h \pm 1 h), Day 85 (predose -1 h and postdose 4 h \pm 1 h), and Day 113 (any time during the visit). During the Follow-up Period, 1 sample will be collected on Days 141, 169, and 197 (any time during the visit) [Table 3].

A large rectangular area of the page is redacted with black ink, obscuring several lines of text. To the left of this redacted area, there are four small, vertical black squares arranged in a column.

CONFIDENTIAL

The information contained herein may not be used, disclosed, or published without the written consent of Biogen MA Inc.

Table 3: Pharmacokinetic Assessments

Study Week	0	1	2	4	8	12	16	20	24	Follow-Up Period

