- The chest X-ray was removed as a requirement for both Part A and Part B, and a footnote on tuberculosis testing was added to Table 1 and Table 2: “⁵Testing to be performed locally. Indeterminate Quantiferon or T-SPOT tests may be repeated once and will be considered positive if retest results are positive or indeterminate. Subjects with documented BCG vaccination must perform a TB test at Screening and will be excluded if they exhibit skin induration ≥ 5 mm or a positive Quantiferon or positive or borderline T-SPOT (Elispot) test.” For further information, see the change to exclusion criterion 16 (Section 8.2) below.
- Urine Pregnancy Test: An assessment was added at Week 2.
- A footnote was added to the Physical Examination, Weight, and Height assessment in Table 1 and Table 2: “⁷Height should be measured only once; i.e., at the Day 1/baseline visit.”
- For the Vital Signs assessment, it was clarified in footnote 8 to Table 1 and Table 2 that oral body temperature should be measured.
- [REDACTED]
- [REDACTED]
- [REDACTED]
- [REDACTED]
- Joint count assessments were added to Table 1 at Screening and Weeks 2, 4, 8, 16, 20, and FU12. See detailed explanations in this document under Primary Reason for Amendment and Section 8.1.2, Inclusion Criteria (Part A Specific).
- The timing of PK assessments was revised in Table 1 and Table 2. In Table 1, assessments were removed at Weeks 2, 8, 20, and FU8. In Table 2, assessments were removed at Weeks 2 and 8. Also, a separate table on PK assessments (Table 3) was added to specify when PK assessments should be done during each visit. The frequency of [REDACTED], complement, skin RNA tape harvesting, [REDACTED], and blood RNA [Paxgene]) was reduced in Table 1 and Table 2.
- The following footnote was added to Table 1 (footnote 15) and Table 2 (footnote 17) to provide more guidance on performing the ESR: [REDACTED]
- A footnote on which vaccine-related immunoglobulin titers will be collected in Part A was added to Table 1: “¹⁹Vaccine-related immunoglobulin titers for tetanus, diphtheria, and *Pneumococcus* will be collected.”
- An electronic diary review of subject-reported questionnaires was added to Table 1 and Table 2.
- The timing of CLASI assessments in Part B was revised (assessments were removed at Week 2). Additional guidance on CLASI assessment and adjudication was provided in the footnote: “⁹CLASI will be assessed by the Investigator or a trained designee at all

CONFIDENTIAL

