4.3. Visit/Analysis Week Definitions

The definition of visits below applies to both parts A and B.

Baseline

Baseline will refer to the last non-missing value prior to the first randomized dose.

Treatment Day [TD] (Days relative to the first randomized dose)

To facilitate the analysis of the data in the treatment period (TP), TD will be calculated for each day in the study as the number of days between the date of the first randomized dose and the specific day of interest. For a day that is on or after the day of the first randomized dose, the TD is a positive value and will be calculated as (date of study day – date of the first randomized dose +1). For a day that is prior to the date of the first randomized dose, the TD is a negative value and will be calculated as (date of study day – date of the first randomized dose). The study starts at TD1.

Analysis Week

Observations that are collected after the first randomized dose as scheduled visit will be used to the corresponding analysis week. Baseline corresponds to “Week 0” in the protocol or the latest non-missing value prior to first study drug administration if Week 0 assessment is missing.

Data from Early Termination or Unscheduled Visits

In general, when data are summarized by visit/analysis week, the Early Termination Visit or Unscheduled Visit will be assigned to an appropriate scheduled visit/analysis week (PV2 or later) by using a window scheme as follows.

CONFIDENTIAL

The information contained herein may not be used, disclosed, or published without the written consent of Biogen MA Inc.

The lower bound and the upper bound for the visit windows are defined as the midpoints of the scheduled visits (PV2 or later). If the date and time from early termination visit falls in between the lower bound and the upper bound for a scheduled visit, then it will be assigned to that visit. If there are 2 or more assessments available in the same analysis window for a subject, the assessment that is closest to the target visit day will be used for analysis. If there are 2 or more assessments in the same analysis window with the same distance from the target visit day, the earlier assessment will be used.

The windowing scheme for the primary endpoint in Part A and Part B is shown in [Table 2](#) and [Table 3](#) below.

CONFIDENTIAL

The information contained herein may not be used, disclosed, or published without the written consent of Biogen MA Inc.

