Table 2 Visit Windows for Primary Endpoint (Joint Count) in Part A

Analysis visit	Target visit day	Analysis visit window
Baseline (Week 0)	1	Most recent non-missing pre-dose value
Week 2	15	[2, 22]
Week 4	29	[23, 43]
Week 8	57	[44, 71]
Week 12	85	[72, 99]
Week 16	113	[100, 127]
Week 20	141	[128, 155]
Week 24	169	[156, 197]
Follow-up 12	253	≥ 198

Table 3 Visit Windows for Primary Endpoint (CLASI) in Part B

Analysis visit	Target visit day	Analysis visit window
Baseline (Week 0)	1	Most recent non-missing pre-dose value
Week 2	15	[2, 22]
Week 4	29	[23, 43]
Week 8	57	[44, 71]
Week 12	85	[72, 99]
Week 16	113	[100, 141]
Follow-up 12	197	≥ 142

*For Part B subjects in PV1 who didn't reconsent to PV2 and hence don't have week 16 visit, the follow-up period days and lower and upper bound of visit window will shift back by 28 days

CONFIDENTIAL

The information contained herein may not be used, disclosed, or published without the written consent of Biogen MA Inc.

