6. EFFICACY ANALYSES

6.1. General Considerations

For both Part A and Part B, the efficacy analyses will be performed using the MITT population and will be considered as the primary analyses. For each endpoint, additional conditions may apply for pooling of data across protocol versions (see [Section 3.1](#)). The final model for each analysis in the MITT population will also be used for the PP analysis. A complete list of all the planned analyses and target population for the primary and secondary endpoints is provided in [Appendix A1](#) (Part A) and [Appendix A2](#) (Part B).

Unless otherwise specified, statistical testing across all efficacy endpoint will be performed to compare each BIIB059 dose (Part A: 450 mg; Part B: 50, 150 or 450 mg) with placebo at the 2-sided, 0.05 significance level. P-values and corresponding 95% confidence intervals (CI) will be provided. P-values will be rounded to three decimal points before assessing statistical significance.

CONFIDENTIAL

The information contained herein may not be used, disclosed, or published without the written consent of Biogen MA Inc.

 Biogen	Statistical Analysis Plan 230LE201	<V 2.0>
--	---	----------------------

Summary statistics will be presented for all endpoints at all visits including follow-up visits. For continuous variables, the summary statistics will include number of subjects with data, mean, standard deviation (SD), median, first quartile (Q1), third quartile (Q3), minimum and maximum. For categorical endpoints, the summary statistics will generally include: number of subjects in the corresponding analysis population, number and percentage of subjects in each category.

Unless otherwise specified, week 2, 4, 8, 12, 16, 20 and, 24 will be included in all Part A “by visit” MMRM analyses.

Unless otherwise specified, week 2, 4, 8, 12 and, 16 will included in all Part B “by visit” MMRM analyses.

Additional study part specific efficacy analyses considerations are described in [Section 6.1.1](#) (Part A) and [Section 6.1.2](#) (Part B)

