Intermittent (non-monotonic) missing data will be imputed based on the MAR assumption and with an imputation model using Markov chain Monte Carlo (MCMC) method within each treatment group. The imputation models will include baseline value and the values at each post-baseline week for endpoint of interest. The MCMC method in the MI procedure in SAS will be used with a single chain, with a burn-in of 1000, and a thinning of 100 and non-informative priors for all parameters.

The remaining, monotonic missing data for all subjects who discontinue study treatment early will be imputed using sequential regression MI model estimated based on data from the placebo group only. Each sequential regression model (i.e., for imputation of values at a given week) will include terms for baseline score, the stratification factors, and all the continuous endpoint scores. Missing values at a given week in placebo and BIIB059 groups will be imputed from the same imputation model. No rounding or range restrictions will be applied to imputed continuous values.

200 imputations will be performed. Each of the 200 imputed datasets will be analyzed using the following method.

Results from analysis of each imputed dataset, i.e., least square (LS) mean differences from placebo and their SEs, will be combined using Rubin's method [\[Rubin 1987\]](#) as implemented in the SAS MIANALYZE procedure to produce a pooled LS mean estimate of treatment difference, its 95% CI, and a pooled p-value. A p-value will only be presented for the primary

CONFIDENTIAL

The information contained herein may not be used, disclosed, or published without the written consent of Biogen MA Inc.

comparison at primary timepoint. The LS means of change from baseline to each post-baseline week will be plotted by treatment group.

A figure of the change from baseline to the primary timepoint will be presented; for data imputed using the MI methodology described above the least square mean of the 200 imputed values will be used.

A few subjects from PV1 part B might have completed treatment up to week 12 but could not reconsent to PV2 and therefore will have missing week 16 data. These subjects' week 16 data will be considered MAR and imputed using MMRM.

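### Part B CLASI analyses include a Week 2 visit at which the current schedule has no CLASI, leaving Week 2 inestimable at 50 mg and 150 mg and the sensitivity imputation without usable Week 2 data there

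*SAP*

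**What the plan says.** Three places in the SAP make Week 2 a Part B CLASI analysis visit.

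- SAP 6.1 sets a general rule for by-visit MMRM analyses: "week 2, 4, 8, 12 and, 16 will included in all Part B".
- SAP 6.1.2 repeats the list for the Part B continuous model: "study visit (week 2, 4, 8, 12, 16". SAP 6.2.1 applies that model to percent change in CLASI-A, the primary endpoint.
- SAP 4.3 contains "Table 3 Visit Windows for Primary Endpoint (CLASI) in Part B", with a Week 2 row (target day 15, window 2 to 22). The stated rule is: "The lower bound and the upper bound for the visit windows are defined as the midpoints of the scheduled visits (PV2 or later".

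SAP 6.2.2 names one sensitivity analysis of the primary endpoint, reference-based multiple imputation. SAP 6.6.1 imputes intermittent gaps by MCMC separately in each treatment group, with non-informative priors. It adds: "The imputation models will include baseline value and the values at each post-baseline week for endpoint of interest".

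The CLASI row of protocol Table 2 has no mark at Week 2. The Version 2 amendment summary agrees: "The timing of CLASI assessments in Part B was revised (assessments were removed at Week 2".

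**The concern.** The SAP analyses a CLASI visit that the current protocol does not schedule. Version 1 subjects are pooled in, so the visit is not empty overall. It is populated very unevenly: a minority of the 450 mg and placebo arms, and no scheduled values at 50 mg or 150 mg, which did not exist in Part B under Version 1.

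Two things are at stake. The MMRM carries treatment-by-visit terms that it cannot estimate. The within-arm imputation is asked to model a variable that is essentially unobserved in two of the three active arms. If a programmer drops Week 2 at analysis, that is a sensible repair, but an undocumented departure made after unblinding is possible.

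**Working it through.** **1. Is there a Week 2 CLASI in the current schedule?** In the text available to me the Table 2 CLASI row seems shifted at the left: Screening is blank and Week 1 is marked. Yet Screening CLASI is required, since "CLASI scores at Screening will be verified by an Independent CLASI Adjudicator to confirm eligibility". Moving the first two marks to Screening and Week 0 resolves this. Week 2 is blank on either reading, and Weeks 4, 8, 12 and 16 are marked.

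**2. Reproducing Table 3.** With target days 15, 29, 57, 85 and 113, the midpoints are:

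- (15 + 29)/2 = 22
- (29 + 57)/2 = 43
- (57 + 85)/2 = 71
- (85 + 113)/2 = 99

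These match the Table 3 bounds between Weeks 2 and 16. The bound of 22 arises only if day 15 is a scheduled CLASI visit. Under Version 2 or later, which is the SAP's own reference for windows, it is not.

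**3. Who can have a scheduled Week 2 CLASI?**

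| Arm | Version 2+ (about 25 per arm) | Version 1 planned (SAP 2.1) | Possible scheduled Week 2 CLASI |
|---|---|---|---|
| Placebo | 25 | 10 | 10 of 35 |
| 50 mg | 25 | 0 | 0 of 25 |
| 150 mg | 25 | 0 | 0 of 25 |
| 450 mg | 25 | 20 | 20 of 45 |

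The total is at most about 30 of 130.

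**4. Primary MMRM.** Four arms by five visits gives 20 cells, of which 2 have no scheduled data. An unstructured 5 × 5 covariance has 5 × 6/2 = 15 parameters. Five involve Week 2 (one variance, four covariances) and rest on at most about 30 subjects. A row-space check of the fixed-effects design, using the counts above, gave:

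- Week 2 versus placebo: not estimable for 50 mg or 150 mg, estimable for 450 mg.
- Weeks 4, 8, 12 and 16 versus placebo: estimable for all three doses.

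**5. Convergence.** One scenario was simulated with these counts. It assumed SD 30, within-subject correlations of about 0.39 to 0.54, half of the Version 1 subjects without Week 16, and 20% dropout. The unstructured REML fit converged in 40 of 40 runs, both with and without Week 2. The Week 16 standard error for 450 mg versus placebo was 7.76 with Week 2 and 7.84 without, and the estimate moved by about 1.0 point on average. A repeat with separate code also converged in every run, with a similar shift.

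**6. Imputation.** I ran multivariate-normal data augmentation with a Jeffreys prior in one arm (n = 25, baseline plus five weeks). With Week 2 wholly missing, the covariance draw ceased to be positive definite on both seeds. The same happened with one, two or five Week 2 values. The chain ran with Week 2 fully observed and with Week 2 removed.

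The reason is a simple count. Regressing Week 2 on baseline and four other weeks needs 5 slopes plus an intercept, so 6 coefficients. At the planned 20% dropout an arm of 25 has 0.20 × 25 = 5 early leavers. Even if all five had a CLASI in days 2 to 22, five values cannot identify six coefficients, and a non-informative prior adds nothing.

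**The case against.** The best defence is that SAP 6.6.1 never names Week 2. A week at which CLASI was never scheduled is not naturally intermittent missing data, and if the weeks are limited to those scheduled, the imputation runs. That stands, and it is why a reader should not infer that the sensitivity analysis is impossible. Against it, SAP 6.1, 6.1.2 and the CLASI-specific Table 3 all list Week 2, and no visible text exempts CLASI.

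Other points also have weight:

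- SAP 4.3 assigns early-termination and unscheduled visits to windows, so a few Week 2 values could arise at 50 mg or 150 mg. The accurate statement is no scheduled values. SAP 6.6.1 also censors data after treatment discontinuation, so few would survive.
- The collapse was shown in a purpose-written sampler. The SAS MI procedure that the SAP names was not run.
- The lists in 6.1 and 6.1.2 are general and allow exceptions. They suit endpoints assessed at Week 2, such as PGA in Part B subjects with SLE. Appendix A2 and SAP 6.8 and 6.9 are not readable in the public copy, so an exception there cannot be excluded.
- A reader might infer that a nearly empty visit threatens the primary test. The documents do not support that: Week 16 contrasts are estimable, 6.1.2 pre-specifies two fallback covariance structures, and the simulated scenario showed no convergence failure.

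**Conclusion.** The mismatch is real and lies in the operative SAP text. Week 2 CLASI contrasts for 50 mg and 150 mg cannot be estimated from scheduled data. The within-arm imputation, read together with the SAP's visit lists, would not be expected to run in those arms unless Week 2 is left out. This affects the one missing-data sensitivity analysis that SAP 6.2.2 names for the Part B primary endpoint; SAP 6.10 says the retrieved-dropout analysis does not count as one.

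The Week 16 MMRM and MCP-Mod contrasts remain estimable and should change little. Convergence trouble is possible, but the single scenario examined neither showed it nor rules it out. The conclusion assumes the planned Version 1 numbers and allocation, and few CLASI values from unscheduled or early-termination visits in days 2 to 22. It is a specification error that should be corrected before database lock, not a threat to the primary test.

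**What to change.** For Part B CLASI endpoints only:

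- Name Weeks 4, 8, 12 and 16 as the MMRM visits in SAP 6.1 and 6.1.2 and as the imputation weeks in 6.6.1. Keep Week 2 for endpoints scheduled then, such as PGA.
- Delete the Week 2 row from Table 3 and state the Week 4 lower bound explicitly. Starting at day 2 would label a very early termination value as Week 4. Keeping day 23 avoids this. The midpoint with baseline, (1 + 29)/2 = 15, would give day 16.
- Summarise Version 1 Week 2 CLASI values descriptively.

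The cost is wording plus a little information. Version 1 Week 2 values would no longer inform the MMRM, including its predictions for Version 1 subjects without Week 16. A subject whose only post-baseline CLASI is at Week 2 would leave the primary analysis set; the SAP should say so and report how many there are. A side benefit is that the remaining visits are equally spaced, which suits the Toeplitz fallback.
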